10 DIETARY MANAGEMENT

Occurrence of dietary modification and reason for modification will be listed.

11 COMPLIANCE

Treatment compliance will be summarized by age group at enrollment and all ages combined. In addition, the treatment compliance will be summarized in 3 categories: <80%, 80% - 120% (inclusive), and > 120%. The compliance to study drug will be measured in the following parameters:

- Treatment compliance based on prescribed dose taken

Formula:
$$\frac{\text{Total Kuvan Intake}}{\text{Total Kuvan Prescribed}} \times 100\%$$

The total amount of Kuvan intake (measured in mg) will be calculated by multiplying the actual dose of daily Kuvan taken by the duration of the dosing period and then summing across all dosing periods. The total amount of Kuvan prescribed will be determined by multiplying the prescribed daily Kuvan by the duration of the dosing period and then summing across all dosing periods. The duration of a dosing period is defined as the subject’s medication stop date minus the medication start date plus 1 for each dosing period.

- The percentage of days on correct dosage

Formula:
$$\frac{\text{Number of Days with Correct Dose Intake}}{\text{Total Days of All Dose Periods}} \times 100\%$$

The numerator is the total number of days the subject took the same amount of study drug as the prescribed dose. The total days of all dosing periods will be calculated by summing the durations of all dosing periods.

B:OMARIN™	SAP PKU-015, Version 3.0	Page 20 of 31
-----------	--------------------------	---------------

- The percentage of days on drug

Formula:
$$\frac{\text{Number of Days with Kuvan Intake}}{\text{Total Days of All Dose Periods}} \times 100\%$$

The numerator is the number of days the subject took Kuvan, regardless of the amount taken. The total days of all dosing periods will be calculated by summing the durations of all dosing periods.

- Actual daily dose taken (mg/kg/day)

The parameter will be calculated as the mean of daily dose from all dosing periods. Daily dose from each dosing period will be calculated by sum of total amount of Kuvan intake in mg, divided by dosing weight, and the duration of the dosing period.

A subject listing of treatment compliance will be provided.

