3.2 Study Design

This 2-part, multicenter, open-label study is designed to evaluate the safety of Kuvan and its effect on neurocognitive function, blood Phe concentration, and growth in children with PKU when treatment is initiated at 0-6 years of age. The study will be considered complete when approximately 45 subjects have completed 7 years of treatment.

One of the goals of the study will be to decrease blood Phe levels to reach a goal of ≤ 240 $\mu\text{mol/L}$. Subjects will meet with a dietician at each study visit to review dietary Phe intake. Dietary Phe may be added to the diet, at the discretion of the Investigator, if a blood Phe level falls below 120 $\mu\text{mol/L}$ or decreased if blood Phe level is above 240 $\mu\text{mol/L}$. If a subject's blood Phe falls below 120 $\mu\text{mol/L}$, at the discretion of the investigator, a gradual increase of approximately 5-20 mg/kg of Phe supplement may be added to the diet. If a subject's blood Phe level goes above 240 $\mu\text{mol/L}$, dietary Phe may be decreased by

	SAP PKU-015, Version 3.0	Page 7 of 31
---	--------------------------	--------------

approximately 5 to 20 mg/kg or defined by the standard used at each treatment center, at the discretion of the investigator.

Part 1: Evaluation of Kuvan Responsiveness

Beginning at Week 0 and after all baseline assessments are completed, subjects enrolled into the study will receive 20 mg/kg Kuvan daily for 4 weeks. Subjects will return to the clinic weekly for safety assessments and blood Phe concentration measurement. Subjects should continue with their current amount of dietary Phe intake. However, if a subject's blood Phe concentration drops below 120 $\mu\text{mol/L}$, at the discretion of the Investigator, a gradual increase by approximately 5 to 20 mg/kg of daily dietary Phe supplement may be added to the diet. It is important to avoid unstable swings in blood Phe concentrations. No dose adjustments can be made during Part 1 without consultation with the Medical Monitor.

Part 2: Neurocognitive Study

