Subjects who are responsive to Kuvan will continue to receive once a day doses of 20 mg/kg Kuvan orally. A Kuvan-responsive subject is defined as a subject with $\geq 30\%$ average reduction in blood Phe concentration calculated by the mean of the weekly percent change from baseline in blood Phe concentration at Weeks 1, 2, 3 and 4. The baseline blood Phe concentration is calculated as the mean of the results from Screening visit and at Week 0 (prior to dosing with Kuvan). At the discretion of the Investigator, the subject's daily Phe intake may be modified if blood Phe concentration falls below 120 $\mu\text{mol/L}$ during the study. Kuvan dose may also be reduced after Week 5 after consultation with the Medical Monitor, in subjects who do not tolerate the 20 mg/kg/day dose.

Neurocognitive testing will be performed within 6 weeks of determination of Kuvan responsiveness in all Kuvan-responsive subjects. The types of neurocognitive tests used (Bayley Scales of Infant and Toddler Development®-Third Edition [Bayley-III], Wechsler Preschool and Primary Scale of Intelligence™-Third Edition [WPPSI-III], and/or Wechsler Intelligence Scale for Children®-Fourth Edition [WISC-IV]) will be those appropriate for the subject's current age at assessment. Table 3.2.1 shows the neurocognitive test to be used according to subject age.

	SAP PKU-015, Version 3.0	Page 8 of 31
---	--------------------------	--------------

Table 3.2.1: Neurocognitive Assessments

Age Group	Infancy	Preschool		School-Age
Assessment	Bayley-III	WPPSI-III (First Form)	WPPSI-III (Second Form)	WISC-IV
Age	0 months through < 30 months	30 months through < 4 years	≥ 4 years through < 7 years	≥ 7 years and older
Frequency	Every 6 months ± 2 weeks	Once a year ± 2 weeks	Once a year ± 2 weeks	Every 2 years ± 2 weeks

Growth, blood Phe concentration, and safety will be monitored. These and the neurocognitive assessments will be performed every 6 to 24 months, depending on the type of assessment, until the end of the study.

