12 EXTENT OF EXPOSURE TO STUDY DRUG

The duration over which subjects took Kuvan will be derived from the study drug exposure Case Report Form (CRF). The durations of exposure are the sum of days that the subject took Kuvan. Descriptive statistics for total duration will be provided by age group at Screening, study part, and overall. The number of dose changes and the reasons for the changes will be summarized as well.

A by-subject listing of each subject's extent of exposure and dose changes will be provided.

	SAP PKU-015, Version 3.0	Page 21 of 31
---	--------------------------	---------------

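### Actual daily dose (mg/kg/day) is a plain mean over dosing periods, so it can misstate a child's average dose when periods differ in both length and mg/kg dose

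*SAP*

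**What the plan says.** SAP Section 11 (Compliance) lists four parameters. For the fourth, actual daily dose in mg/kg/day, it gives two steps. Within a period: "Daily dose from each dosing period will be calculated by sum of total amount of Kuvan intake in mg, divided by dosing weight", and divided also by the length of that period. Across periods: "The parameter will be calculated as the mean of daily dose from all dosing periods". No weights are mentioned. The length of a period is the "medication stop date minus the medication start date plus 1 for each dosing period", so nothing makes periods equal.

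The other three parameters keep track of time. Total intake, the numerator of the intake/prescribed ratio, comes from "multiplying the actual dose of daily Kuvan taken by the duration of the dosing period and then summing across all dosing periods", and the prescribed total is built the same way. Both percentage-of-days measures divide by the total days of all dosing periods.

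Three statements elsewhere set the context:
- Section 3.2, Part 1: "subjects enrolled into the study will receive 20 mg/kg Kuvan daily for 4 weeks".
- Section 3.2, Part 2: "Kuvan dose may also be reduced after Week 5 after consultation with the Medical Monitor", for subjects who do not tolerate the starting level.
- Section 3.2, opening: "The study will be considered complete when approximately 45 subjects have completed 7 years of treatment".

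Section 12 adds: "The number of dose changes and the reasons for the changes will be summarized as well". It also provides a by-subject listing of exposure and dose changes, but no average dose.

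**The concern.** Once each period's dose has been divided by that period's own duration, a plain mean gives a period of a few weeks the same weight as one of several years. The plan allows a dose change soon after the start of a course that may last seven years, so short and long periods at different doses can sit side by side in one child's record. The result then depends on how the dosing form happens to be split into records as well as on what the child took.

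What is at stake is the description of treatment actually received. This is the only place where the SAP summarises dose in mg/kg/day, and a reader of the study report would naturally take it as the average dose over the course.

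**Working it through.** The SAP gives no average dose, so there is no stated figure to reproduce. The check compares the rule as written with the time-averaged dose.

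**Inputs from the SAP:** starting level 20 mg/kg (Section 3.2); reduction possible after Week 5, taken as 35 days; 7 years of treatment, taken as 7 × 365 = 2,555 days.

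**Assumed, for arithmetic only:** reduced levels of 90%, 75% and 50% of the starting level, and the way records are split. The SAP states neither.

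**Formulas**, with dᵢ the mg/kg/day in period i, nᵢ its days and k the number of periods:
- Rule as written: U = Σdᵢ / k
- Duration-weighted mean: W = Σdᵢnᵢ / Σnᵢ
- Difference: U − W = −cov(dᵢ, nᵢ) / mean(nᵢ), the covariance being taken over the k periods with divisor k. It is zero if all nᵢ are equal or all dᵢ are equal. Otherwise it depends on whether the short periods are the high-dose or the low-dose ones.

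**Worked case, 50%, two records** (35 days at 20, then 2,520 days at 10):
- U = (20 + 10) / 2 = 15.00
- W = (35 × 20 + 2,520 × 10) / 2,555 = 25,900 / 2,555 = 10.14
- U / W − 1 = +48.0%

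**All cases** (U against W in mg/kg/day, then relative error):

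| Record structure | 90% | 75% | 50% |
|---|---|---|---|
| 35 days at start, then one long reduced period | 19.00 v 18.03, +5.4% | 17.50 v 15.07, +16.1% | 15.00 v 10.14, +48.0% |
| Same, reduced phase as 14 six-month records | 18.13 v 18.03, +0.6% | 15.33 v 15.07, +1.8% | 10.67 v 10.14, +5.2% |
| 30-day reduction between periods of 1,200 and 1,325 days | 19.33 v 19.98, −3.2% | 18.33 v 19.94, −8.1% | 16.67 v 19.88, −16.2% |
| Change at mid-study, two equal periods | 0% | 0% | 0% |

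If mg changes only to follow weight and mg/kg stays constant, every dᵢ is the same and the error is 0%.

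**Records that follow visits.** Table 4.5.1 schedules weight and vital signs at Weeks 1 to 4, Months 2 to 6, and every six months after that. If dosing records followed those visits (an assumption), 4 + 5 = 9 periods would fall in the first 6 months and (84 − 6) / 6 = 13 afterwards. Then 9/22 = 41% of the weight would rest on 6/84 = 7% of the time. For a change after Month 6, as a share of the starting level:
- To 50%: U = (9 + 13 × 0.5) / 22 = 70.5%; W = (6 + 78 × 0.5) / 84 = 53.6%; error about +32%.
- To 75%: U = (9 + 13 × 0.75) / 22 = 85.2%; W = (6 + 78 × 0.75) / 84 = 76.8%; error about +11%.

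**The case against.** The strongest reply is that the size of the error rests on a record structure the SAP does not describe. A reader might infer that the four-week Part 1 period is set against a single multi-year Part 2 period. Nothing says Part 2 is one period. Dosing is per kg in growing children and each period uses a dosing weight, so many shorter records are at least as plausible. With six-month records after the first, a halving at day 35 gives about 5% rather than 48%. This part of the reply stands, and the 48% figure is an extreme.

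A reader might also infer that every child with a dose change gets a wrong figure. The documents do not support that. A change in mg that only tracks weight leaves mg/kg unchanged and causes no error, and neither do periods of equal length.

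It can be added that an unqualified mean is under-specified and a programmer might weight it, that a mean of period doses and an intake/prescribed ratio are different quantities, and that Section 12 keeps dose changes visible. These points lower the stakes but do not justify the formula. The literal reading is a plain mean, and shorter records do not by themselves cure it: with records that follow the Table 4.5.1 visits, a halving after Month 6 still gives about +32%.

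**Conclusion.** The point holds in limited form. As written, the actual daily dose ignores period length, unlike its three companion parameters, and can be wrong in either direction when length and mg/kg dose both vary between periods. In the assumed cases the error runs from 0% to about +48% for an early lasting reduction and from about −3% to −16% for a short temporary one. These figures rest on assumed dose changes and record splits. They are not estimates of what the trial will show.

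A reader might infer that the efficacy or safety conclusions are affected. They are not: the parameter does not enter the FSIQ analyses, the intake/prescribed ratio or the exposure-adjusted adverse-event rates. It is one descriptive summary, worth correcting because it is the SAP's only statement of dose received in mg/kg/day.

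**What to change.** In Section 11, define actual daily dose as Σ(mg taken in the period / dosing weight for that period) divided by the total days of all dosing periods. This is the duration-weighted mean W above. Splitting a period into several records at the same daily mg and dosing weight leaves it unchanged. It would also help to state when a new dosing period begins: at a visit, a weight update or a dose change.

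The cost is one sentence in the SAP and about one line of code. Every quantity needed is already required by Section 11, so no new data are collected, and no dose or clinical rule changes.

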12 EXTENT OF EXPOSURE TO STUDY DRUG

The duration over which subjects took Kuvan will be derived from the study drug exposure Case Report Form (CRF). The durations of exposure are the sum of days that the subject took Kuvan. Descriptive statistics for total duration will be provided by age group at Screening, study part, and overall. The number of dose changes and the reasons for the changes will be summarized as well.

A by-subject listing of each subject's extent of exposure and dose changes will be provided.

	SAP PKU-015, Version 3.0	Page 21 of 31
---	--------------------------	---------------

13 EFFICACY EVALUATIONS

Unless specified otherwise efficacy analyses will be based on the efficacy population. The efficacy results will be presented by age group at Screening and by all ages combined, except for the neurocognitive assessments.

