3.6 Interim Analysis

There is no formal interim analysis planned. However, an analysis of data for a subset of subjects who responded to sapropterin therapy and had completed at least 2 years in the study as of June 2012, including subjects who terminated early from the study prior to reaching their 2-year study visit, was performed. Neurocognitive function, blood and dietary Phe control, growth assessments, and adverse events were examined.

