4.1 Analysis Populations

The Full Analysis set (FAS) will consist of all subjects who enroll into the study.

The Enrolled population will consist of all subjects who enter Part 2 of the study and met the inclusion/exclusion criteria per CRF. This population involves subjects who respond to Kuvan and had a Bayley-III or IQ test score ≥ 80 within 6 weeks of determination of Kuvan responsiveness in Part 1. Kuvan responders consist of all subjects with at least 30% average reduction in blood Phe concentration calculated as the mean of the weekly percent change from baseline at Week 1, 2, 3 and 4 in Part 1.

The Efficacy population will consist of all subjects from the Enrolled population who have at least two WPSI/WISC assessments.

The Safety population will consist of all subjects who have received any study drug in the FAS population.

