13.2 Secondary Endpoints

The secondary efficacy variables are:

- Growth measurements (height, weight, head circumference z-scores)
- Neurocognitive testing results (Bayley-III) in children age 0 to less than 30 months old.

A subject listing of Bayley-III results and growth parameters (height, weight, and head circumference assessments and corresponding percentile and z-score) will be provided..

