13.2.1 Growth Measurements

The change in height, weight, and head circumference from baseline will be assessed at each scheduled visit. In addition, height, weight, and head circumference will be converted to z-score based on CDC Clinical Growth Charts (WHO Growth Charts for subjects less than 24 months) and the percentile, z-scores, and change in z-score from baseline of these growth variables will be summarized for each age group and all ages combined at each schedule time point. Growth charts using z-scores will be provided in each scheduled time point.

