13.2.2 Neurocognitive Testing (Bayley-III)

The change in each composite score from baseline will be assessed at each scheduled visit. The three composite measures are cognitive, language, and motor. Only subjects less than 30 months of age are considered.

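### The default Efficacy population requires two WPPSI/WISC tests, so the Bayley-III and growth summaries count infant entrants only if they stay to about 42 months of age

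*SAP*

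**What the plan says.** Section 13 opens with a default: "Unless specified otherwise efficacy analyses will be based on the efficacy population". Section 4.1 defines that set: "The Efficacy population will consist of all subjects from the Enrolled population who have at least two WPSI/WISC assessments" (WPSI is read here as WPPSI).

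Section 13.2 lists the secondary efficacy variables as growth and "Neurocognitive testing results (Bayley-III) in children age 0 to less than 30 months old". For growth, section 13.2.1 says "The change in height, weight, and head circumference from baseline will be assessed at each scheduled visit". For Bayley-III, section 13.2.2 says "The change in each composite score from baseline will be assessed at each scheduled visit", and then limits the analysis by age to children under 30 months. Neither section names an analysis population. Nor do the exploratory sections 13.3.2 (blood Phe) and 13.3.4 (prescribed dietary Phe).

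Table 3.2.1 in section 3.2 uses Bayley-III below 30 months of age. The first WPPSI-III form covers "30 months through < 4 years" and is given "Once a year ± 2 weeks". Section 4.7 rules out imputation of missing efficacy data.

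**The concern.** Bayley-III stops at 30 months of age, but entry to its summary table depends on a different test battery, the second sitting of which normally falls a year after that. Height, weight, head circumference and Phe are measured from the start, yet their summaries carry the same condition. Whether a child counts at Month 6 or Month 12 is therefore decided by something that happens later.

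Two things are at stake. First, precision: valid early measurements from children who leave are dropped from the tables. Second, selection: those who remain are the children whose families stayed. If leaving is related to development, growth or Phe control, the reported mean changes are biased in a direction that the plan gives no way to judge. The filter also differs by entry age, so the youngest age groups and the all-ages growth summary rest on unequal retention requirements.

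**Working it through.** **Plan's own figures.** The SAP gives no figure for this exclusion and no dropout rate. Its one sample-size figure (section 3.4) reproduces. The SD of the paired difference is 16 × √(2 × (1 − 0.8)) = 10.12. With 45 subjects and a 5-point margin, power is 91.2% by the normal approximation and 90.0% by the noncentral t. That calculation concerns FSIQ and plays no part below.

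**Step 1: does any text override the default?** No. The under-30-months rule in section 13.2.2 restricts age within whatever set applies. The age groups in section 4.2 govern presentation. No section from 13.2.1 to 13.2.2, and neither 13.3.2 nor 13.3.4, names another population.

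**Step 2: earliest scheduled age at the second WPPSI-III.** 30 + 12 = 42 months, or about 41.5 months with the 2-week tolerance. Section 4.1 sets no minimum gap between tests, so an off-schedule second test could qualify a child somewhat earlier.

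**Step 3: retention needed** = 42 months − age at entry.

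| Entry age | Retention needed |
|---|---|
| 0 months | 42 months (3.5 years) |
| 12 months | 30 months (2.5 years) |
| 24 months | 18 months (1.5 years) |

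By contrast, a child who enters at 30 months or older and stays in the yearly WPPSI-III range can qualify with the Month 2 test and one a year later: 2 + 12 = about 14 months.

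**Step 4: who is excluded by schedule alone?** A child who leaves before 24 months on study cannot have two tests if entry age + 24 < 42, that is, entry before 18 months of age (about 17.5 with the tolerance). Such a child cannot have even one if entry age + 24 < 30, that is, entry before 6 months. As an example, a birth entrant with complete Month 6 to Month 24 Bayley-III and growth data who leaves at 35 months of age appears in none of those summaries.

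**Step 5: illustrative size.** Assume a constant loss rate r per year; the share excluded is 1 − exp(−r × years needed).

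| Assumed r | Entry at 0 | Entry at 12 months | Entry at 24 months |
|---|---|---|---|
| 0% | 0% | 0% | 0% |
| 2% | 6.8% | 4.9% | 3.0% |
| 5% | 16.1% | 11.8% | 7.2% |
| 8.2% | 25.0% | 18.5% | 11.6% |

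The top rate is what would shrink 80 enrolled (upper end of section 3.4) to 45 after 7 years (section 3.2): ln(80/45)/7 = 0.082. Starting from 60 gives ln(60/45)/7 = 0.041, which excludes 1 − exp(−0.041 × 3.5) = 13% of birth entrants. Neither is a dropout rate stated by the plan: the 60 to 80 also serves precision, and 45 is the number at which the study is considered complete.

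**Step 6: how much is recoverable for Bayley-III?** A child who leaves before a first post-baseline test has no change score in any population. Taking that test at Month 6, the recoverable share of birth entrants at the top rate is exp(−0.082 × 0.5) − exp(−0.082 × 3.5) = 0.960 − 0.751 = about 21%.

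**The case against.** The strongest case on the other side concerns importance. The affected analyses are descriptive, with no success rule. Subject listings of Bayley-III, growth and Phe are planned, so the data do not vanish from the report. The number of children affected is unknown and could be zero. All of this is right and limits the weight of the point, but a listing does not correct a summary table built on a selected set.

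Some narrower objections also stand in part:

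- The figures for entry at 24 months apply to growth and Phe, and hardly at all to Bayley-III. Table 4.5.1 places the Bayley-III baseline at Day 30 to 120, so such a child is about 25 to 28 months old at baseline, and the next 6-monthly test falls past 30 months.
- The 25% overstates what a wider population would recover for Bayley-III; about 21% is the matching figure.
- The rule binds older children too. WISC-IV is given every 2 years from age 7, so a child first tested on it needs about 2 years. Only entrants below about 18 months of age face a longer requirement than that.
- Section 3.6 describes a June 2012 analysis of neurocognitive function, Phe and growth, "including subjects who terminated early from the study prior to reaching their 2-year study visit". The final plan is not bound to match it. It is useful only as a sign that early leavers' data were thought worth including.

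None of these changes the chain from section 13 to section 4.1 to Table 3.2.1.

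**Conclusion.** The point holds. Followed as written, the SAP makes inclusion in the Bayley-III, growth, blood Phe and dietary Phe summaries depend on a second WPPSI/WISC test. For infant entrants this normally means retention to about 42 months of age. On the schedule, a child who enters before 18 months of age and leaves before the 2-year visit is excluded.

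The number excluded cannot be derived from the SAP. Over an assumed constant loss of 0% to 8.2% per year it is 0% to 25% of birth entrants, 0% to 19% of those entering at 12 months and, for growth and Phe, 0% to 12% of those entering at 24 months. The direction of any bias is unknown. The primary FSIQ conclusion does not change. This should be corrected because the stated rule gives a poorer answer on the secondary endpoints and the remedy is simple.

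**What to change.** Add one sentence to each of sections 13.2, 13.3.2 and 13.3.4, along these lines: growth, Bayley-III, blood Phe and prescribed dietary Phe are analysed in the Enrolled population defined in section 4.1, and change from baseline at a visit uses all members with a baseline and a value of that measure at that visit. Keep the two-test Efficacy population for the FSIQ and other IQ analyses.

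The cost is three sentences and a changed population flag in the affected tables. No new data and no new population are needed. The one drawback is that table Ns will differ between FSIQ and the other endpoints, which a footnote can explain.
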